7.3 Blinding

The double blind study is a procedure in which the subject and treating physician do not know which study subjects were assigned to which treatment group. To achieve blind conditions for the drug product, the investigational drug product and the placebo are both packaged in identical bottles with the same legends on the label. The blinding codes are kept by an individual uninvolved in the study designated by the sponsor. The codes are also available in the research center (completely sealed), so the Researcher may refer to them should a subject present a serious adverse event, after being authorized by the study sponsor. The blind conditions are strictly upheld during the data analysis.

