17. ADVERSE EVENTS

17.1 Adverse event, definition and communication

17.1.1 Overview

Adverse events (EA) may appear during the study, these may be associated or not with the study drug. If at any time any of the subjects may present any adverse event classified as serious that is derived from the drug's administration, the guidelines of the Official Mexican Norm 220 SSA1 2012 Installation and Operation of the Pharmacovigilance shall apply. The administration of the drug will be interrupted and the administration of an alternative therapy will be prescribed, as per the judgement of the main researcher.

An adverse event is any medical occurrence in a subject or subjects of a medical research, to whom a pharmaceutical product was administered and that does not necessarily have a causal relation with this treatment. Therefore. An EA can be any unfavorable and unintended sign (including an abnormal laboratory finding), symptom or disease temporally associated with the use of a medicinal (research) product, whether it is or not related to this.

The researcher must report the adverse events occurred during the study from the moment in which the subject signs the informed consent to be included in the clinical trial until the conclusion of the last procedure described in the approved version of the study protocol.

In all cases the etiology must be identified as far as possible and the sponsor must be notified. An “unexpected adverse event” is understood as any EA that is not identified in the nature, severity or frequency in the Researcher’s Manual or in the information of the risks described in this protocol.

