17.2 Classification and severity

17.2.1 Classification

The adverse events are divided in two categories according to their importance: “serious” and “not serious”, this classification determines the procedures that must be used to report and document the adverse event.

A **serious adverse event** is that which:

- ❖ Threatens the life or causes the death of the subject.
- ❖ Makes it necessary to hospitalize or prolong the hospital stay
- ❖ It is the cause for persistent or meaningful incapacity
- ❖ It is the cause of alterations or malformations in the newly born

A non-serious adverse event is that which does not comply with any of the previous criteria.

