17.5.6 Reporte de los Eventos Adversos Serios

An active search of EAs must be performed using the spontaneous reports of the subject and physical explorations and interviews performed by the researcher during the visits.

If the EA ends up interrupting the study, the researcher must complete the FCR, in the section corresponding to Termination of the study, and specify if the event is serious or not.

A form of serious adverse events must be completed by the main researcher or the physician in charge and sent to the sponsor within the 24 hours following the notification; even if not all the required information is yet available at the moment. All the information gathered afterwards must be sent immediately once it is available. The researcher must provide an adequate and complete follow-up of the EAs. At any time they must provide an updated report of the EAs and report in writing when there is a final result for it.

In the same manner, all the EAs must be reported to the Committees of Ethics in Research, as well as the Regulatory authorities.

All the EAs as per the previous definitions and independently of the treatment or relationship with the study drug must be notified as soon as the event is known.

The researcher must notify the sponsor of the event sending the form "Serious Adverse Event Report" ("first notice") within the 24 hours after knowing about it via email with all the available information on the serious adverse event to the department of Pharmacovigilance of Laboratorios Sophia, S.A. de C.V as well as attaching a copy by email to the monitor in charge of the center.

17.5.7 Pharmacovigilance responsible:

[name] [name].

Email: [contact]

Laboratorios Sophia, S.A. de C.V.

[name]

[name]

[name]

[contact] (Direct)

[name]

[contact]

Direct assistance line, toll-free number: [name]

Non-serious adverse events (mild and moderate) are reported to the regulatory authority by the end of the study (after the report or in the report) and the serious adverse events immediately.

18. MONITORING AND AUDITING PROCEDURES.

Each research center as well as each researcher will have a clinical monitor assigned and authorized to revise, monitor and procure the information obtained from the study subjects.

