Appendix 2. Good Clinical Practices

Good Clinical Practices directives of the International Conference on Harmonization include 13 basic principles, which are based on the Declaration of Helsinki. These principles are as follows:

1. The first principle indicates that clinical trials should be conducted in accordance with ethical principles that have their origin in the Declaration of Helsinki, and that are consistent with Good Clinical Practices and the applicable regulatory requirement(s).
2. The second principle states that before a trial is initiated, foreseeable risks and inconveniences should be weighed against anticipated benefit for the individual trial subject and society. A trial should be initiated and continued only if the anticipated benefits justify the risks.
3. The third principle of Good Clinical Practices indicate that the rights, safety and well-being of the trial subjects are the most important considerations and should prevail over interest of science and society.
4. The fourth principle states that the information available before the trial about an investigational product should be adequate to support the proposed clinical trial.
5. The fifth principle establishes that clinical trials should be scientifically sound, and described in clear, detailed protocol. The requirements of this clinical trial protocol are also described in the directive guidelines of Good Clinical Practices of ICH.
6. The sixth principle indicates that the trial should be conducted in compliance with the protocol that has received prior Institutional Review Board or Independent Ethics Committee approval. This implies that a study can not be started until it has been approved by these institutions.
7. The seventh principle states that the medical care given to, and medical decisions made on behalf of subjects should always be the responsibility of a qualified physician or, when appropriate, of a qualified dentist. The medical care responsible should always be qualified physicians.
8. The eighth principle indicates that each individual involved in conducting a trial should be qualified by education, training, and experience to perform his or her respective task(s). Usually the sponsor is the responsible of ensuring that all the people involved in the performance of the trial are sufficiently trained

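### Section 7.3 makes opening the site's sealed code wait for sponsor authorisation, with no emergency exception or response time, and gives no route for urgent events outside the protocol's definition of serious

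*Combined protocol and SAP*

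**What the plan says.** Section 7.3 (Blinding) defines double blinding as meaning that "the subject and treating physician do not know which study subjects were assigned to which treatment group". On custody it says: "The blinding codes are kept by an individual uninvolved in the study designated by the sponsor". Sealed copies are also held at the research centre, "so the Researcher may refer to them should a subject present a serious adverse event, after being authorized by the study sponsor".

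Section 17.2.1 defines a serious event by four criteria. The first reads "Threatens the life or causes the death of the subject". The others are hospitalisation or a longer hospital stay, persistent or meaningful incapacity, and harm to a newborn. Any event that meets none of these is non-serious. There is no wider category for medically important events.

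For a serious event derived from the drug, section 17.1.1 has administration interrupted and an alternative therapy prescribed, "as per the judgement of the main researcher". Section 17.5.6 has the serious-event form sent to the sponsor "within the 24 hours after knowing about it via email", and section 17.5.7 lists telephone contacts, including a toll-free assistance line. Section 17.3 sends non-serious events to the case report form.

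**The concern.** Codes are kept at a centre so that someone there can open one when a patient's care depends on it. Section 7.3 attaches two conditions: the event is serious, and the sponsor has agreed beforehand. It does not say who at the sponsor authorises, at what hours, how quickly, or what happens if nobody answers.

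At stake is the time it takes a treating physician to learn whether the eye received bromfenac or vehicle, in the cases where that would change what they do. There is also a record-keeping side. The plan does not ask for the date, time or reason of a code break, so the final report could not show how often the blind was broken, or in which arm.

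**Working it through.** No arithmetic applies. The check is a reading of 7.3 against every other place where a code-break rule could stand.

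**Step 1: the conditions in 7.3.** The trigger is a serious adverse event. The precondition is prior authorisation by the sponsor. The word *only* is not in the text, but this is a single permission with a stated precondition.

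**Step 2: search for a second route.**
- 7.5 (randomisation): describes closed envelopes; nothing on opening a code.
- 8.1 to 8.3 (labelling and drug handling): nothing.
- 14 (statistical analysis): a blinded analyst; no handling of unblinded subjects.
- 16.3 and 16.4 (discontinuation, recall): no mention of the code.
- 17.1 to 17.5 (adverse events): interruption, alternative therapy, causality and reporting; no code-break step, exception or time limit.
- 18 (monitoring and audit): no check of the sealed codes.

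**Step 3: apply the text to three situations.**

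| Situation | What the plan provides | Result |
|---|---|---|
| Drug-related serious event, allocation not needed for care | 17.1.1: interrupt the drug, alternative therapy at the researcher's judgement | No obstacle |
| Serious event, allocation would inform care | 7.3: request authorisation, then open | Wait of unstated length |
| Urgent event meeting none of the four criteria, allocation would inform care | Nothing stated | No route, even with sponsor agreement |

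**Step 4: is the third row realistic?** Section 4 names corneal melting among the adverse events of chronic topical NSAID use, and 12.2.3 lists it as a reason to eliminate a subject. An eye with early melting may not yet show lasting incapacity, need not lead to admission, and does not threaten life. It could therefore be non-serious when first seen. Section 4 also reports that three weeks of twice-daily bromfenac appears safe for the ocular surface. That bears on how often this would happen, not on whether a route exists.

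**Step 5: can the delay be computed?** No. The 24 hours in 17.5.6 is an outer limit for reporting a serious event and is not tied to the authorisation in 7.3. A site can telephone sooner. The authorisation time has no stated bound, so no figure can be given.

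**The case against.** The strongest reply is that care does not depend on the code. Section 17.1.1 already lets the drug be interrupted and replaced, neither step needs the allocation, and the sponsor can be telephoned. The codes are also physically on site, so the barrier is procedural. All of this stands, and it confines the point to emergencies in which the allocation would add something. It does not supply an exception or a response time, and a site should not have to deviate from the protocol to obtain information needed for care.

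Several stronger readings are tempting, but the documents do not support them:

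- *That 7.3 contradicts 17.1.1 and the GCP appendix.* Principle 7 in Appendix 2 says that "medical decisions made on behalf of subjects should always be the responsibility of a qualified physician". It concerns responsibility for decisions and does not mention unblinding. Section 17.1.1 leaves therapy to the researcher, and 7.3 does not take that away.
- *That the sponsor can be reached only by email, with a delay of 24 hours or more.* Section 17.5.7 lists telephone contacts, and the 24 hours is a reporting limit.
- *That sponsor involvement breaches the promise in 7.3 to uphold the blind strictly.* That sentence concerns the data analysis, and authorising a code break need not reveal the allocation to the sponsor.
- *That the code is forbidden for non-serious events.* The plan is silent there. The lack of a route is a gap, not a prohibition.
- *That every emergency is affected.* Many need no knowledge of the allocation, and many sight-threatening events could qualify as serious through hospitalisation or incapacity.

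**Conclusion.** The point holds in a limited form. The authorisation condition is a stated rule rather than a missing detail. The available text gives it no emergency exception and no response time, and urgent events outside 17.2.1 have no route at all. Its practical reach is the emergency in which the allocation would inform care. Code breaks should be few, and no sample size, estimate or error rate changes. It is a patient-safety improvement worth making because it is cheap.

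The conclusion assumes that no separate code-break procedure exists outside these documents, for example in the researcher's manual, and that section 7.7 (confidentiality), whose text was not available, contains none.

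**What to change.** In 7.3, replace the prior-authorisation condition with a statement to this effect: the researcher may open that subject's sealed code, without prior sponsor authorisation, when knowledge of the allocation is needed for the subject's urgent care, whether or not the event meets 17.2.1. Then add:

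- The researcher records the date, time and reason, and promptly tells the sponsor that the code was broken. For a serious event this goes with the 17.5.6 form. For any other event it goes in the case report form and a code-break log.
- The allocation is not passed to the monitor or the blinded analyst.
- Assessments made by an unblinded researcher after the break are flagged. This is needed because the plan names no separate assessor: the researcher makes the symptom enquiry (10.4) and evaluates adverse events (10.7).
- The monitor checks the sealed codes at the visits already planned in section 18.
- Code breaks are reported by arm.

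The cost is a short amendment and a log. The downside is a slightly higher chance of an unnecessary code break, limited by the recorded reason and the check of the sealed codes. No dose, treatment rule, sample size or analysis changes.

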7.4 Pharmacological approach

The pharmacological approach consists in the instillation of the ophthalmic solution in the bottom of the conjunctival sac during the waking period in any of the following study groups:

- Group 1:
 - Sodium hyaluronate 0.4 % [Lagricel Ofteno ®] 1 drop 3 times a day in the waking period in the bottom of the conjunctival sac (the following application method is recommended: start: 7:00 ± 1 h; following: 15:00 ± 1 h; end: 19:00 ± 1 h) for 20 days
 - Bromphenac 0.09 % [Zebesten ®] 1 drop 2 times a day in the waking period in the bottom of the conjunctival sac (the following application method is recommended: start: 7:15 ± 1 h; end: 19:15 ± 1 h) for 20 days
- Group 2:
 - Sodium hyaluronate 0.4 % [Lagricel Ofteno ®] 1 drop 3 times a day in the waking period in the bottom of the conjunctival sac (the following application method is recommended: start: 7:00 ± 1 h; following: 15:00 ± 1 h; end: 19:00 ± 1 h) for 20 days
 - Placebo 1 drop 2 times a day in the waking period in the bottom of the conjunctival sac (the following application method is recommended: start: 7:15 ± 1 h; end: 19:15 ± 1 h) for 20 days

7.5 Distribution into treatment groups

The subjects are distributed into the study groups on the visit indicated in the study timetable, through simple 1:1 randomization, closed envelope technique, through a specialized software that uses random number tables to achieve a uniform distribution in each of the treatment groups.

[figure not shown]

Fig. 1. DISTRIBUTION OF STUDY SUBJECTS. Shows the randomized distribution of the study subjects in the research protocol using a computing system through the closed envelope technique.

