7. MATERIALS AND METHODS

7.1 Study design

Multicentric, controlled, randomized, double blind clinical study, which compares the safety and efficacy of Zebesten® for the treatment of conjunctival hyperemia in grade I to III Pterygium compared to placebo.

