7.2 Sample

The total population will be 166 cases, which will be randomly included and distributed in 2 study groups. Both with diagnosis of grade I to III Pterygium.

Subjects with bilateral Pterygium, in which both eyes meet the selection criteria, can participate with both eyes, taking each eye as one case.

Group 1 will receive Zebesten® ophthalmic solution together with Na hyaluronate.

Group 2 will receive placebo (formulation with no drug substance) together with Na hyaluronate.

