12.4 SAMPLE SIZE CALCULATION

Sample size protocol SOPH155-0415/IV

According to the objectives of the study to evaluate the Zebesten ® effect in subjects with primary pterygium, the variables of primary outcome stipulated in the design were:

- Conjunctival hyperemia
- TRL

Both variables are considered, using similar literature, to perform the calculation of the sample size to meet with the study objectives.

Conjunctival hyperemia

The sample size was calculated according to the formula for the continuous quantitative variables:

$$n = 2 \frac{(Z_{\alpha/2} - Z_{\beta})(\delta)}{d^2}$$

With a statistical trust of 95% that corresponds to the type I error, and is the same as 1.96, with a potency of 80% that corresponds to the type II error, and equals to 0.84. It is considered as a standard deviation for the increase of 0.4 degrees of severity1 in the scale of conjunctival hyperemia after a pterygium surgery, with an expected difference of at least 2.9 degrees of severity.

Based on the previous the result was 69 cases (eyes) per group, which was incremented 20% by consideration of the losses (14 subjects), with **a total of 83 cases per group**, with a total population of study of **166 eyes to treat**.⁸

Tear film breakup time

The sample size was calculated according to the formula for continuous quantitative variables:

$$n = 2 \frac{(Z \propto -Z_1 - \beta)(\delta)}{d^2}$$

With a statistical trust of 95% that corresponds to the type I error, and is the same as 1.96, with a potency of 80% that corresponds to the type II error, and equals to 0.84. It's considered as a standard deviation for the increase of 1.47 seconds 2 in the tear film breakup time posterior to 60 days of ciclosporin application A, with an expected difference of at least 10.2 seconds.

Based on the previous the result was of 120 cases per group, which was incremented 20% per consideration to the losses (24 cases), with a total of **144 cases per group**, with a total population of study of **288 eyes to treat**.

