16. IDENTIFICATION PROCEDURES, SECURITY AND THERAPEUTIC ADHERENCE OF THE INVESTIGATION SUBJECTS

16.1 Recruitment

The subject will be recruited in the ophthalmologic consultation of the participating research centers, in which a goal of scrutinized and randomized subjects are contemplated according to their scrutiny and recruitment capacity.

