16.2 Subject identification

All the subject of the study will be identified through a number and their initials.

In the scrutiny stage a number will be assigned to the participant in a consecutive manner, employing 3 digits and once included the subject will be assigned with the subject's number (CFR number) which will be conformed of 3 digits of the molecule, 2 of the center's number, and 3 digits of the consecutive number assigned at the research center.

For example:

155/01/001 (molecule number/ center's number/ subject's number at the center).

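### A multicentre trial with an eye-graded primary outcome uses centre in neither randomisation nor analysis: a cheap gain in precision is missed, but there is no error

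*Combined protocol and SAP*

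**What the plan says.** All references are to the combined protocol and SAP.

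- **Allocation (7.5).** The method is "through simple 1:1 randomization, closed envelope technique, through a specialized software that uses random number tables to achieve a uniform distribution". No block or stratification factor is named. The unit is the subject: "The subjects are distributed into the study groups on the visit indicated in the study timetable".
- **Counting unit (7.2).** Subjects with two eligible eyes "can participate with both eyes, taking each eye as one case". The size is fixed as a total: "The total population will be 166 cases". Section 12.4 gives "a total of 83 cases per group".
- **Centres.** Section 7.1 describes a "Multicentric, controlled, randomized, double blind clinical study". Section 16.1 speaks of centres "in which a goal of scrutinized and randomized subjects are contemplated according to their scrutiny and recruitment capacity", so their sizes will probably differ. The number of centres is not stated. Section 16.2 builds the centre number into each subject number, so centre is already recorded.
- **Outcome.** Hyperemia is graded by comparison with reference images (10.3.2) and is listed in 13.3 as ordinal, by direct observation. Neither section describes central reading or calibration of graders.
- **Analysis (14).** Groups are compared by t test, or by 2x2 tables with chi-squared or Fisher tests. No centre term, stratum or other covariate appears.

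**The concern.** When a grade depends on the observer and each centre has its own observers, part of the spread in hyperemia grades belongs to the centre rather than to the eye. A plain t or chi-squared test counts that part as noise. Simple randomisation also lets one centre put clearly more of its eyes in one arm, so a strict or lenient grader can weigh more on one side by chance. What is at stake is precision on a primary outcome, and how easily a result can be read when a large centre happens to be lopsided. The validity of the test is not at stake.

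**Working it through.** **The plan's own figure.** From 12.4: 69 × 1.2 = 82.8, rounded to 83 per group, and 2 × 83 = 166. That step reproduces. The 69 does not follow from the stated SD of 0.4 and difference of 2.9, since 2 × (2.80 × 0.4 / 2.9)² = 0.3, or 1 per group. That is a separate matter, and nothing below depends on it.

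**Overall split.** Take X ~ Binomial(166, 0.5), treating the 166 eyes as independently allocated.

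- P(exactly 83:83) = 6.2%.
- P(arms differ by 16 or more) = 24%. If every subject were bilateral with both eyes in one arm (83 subjects), this becomes 38%.
- P(70:96 or worse) = 5.2%.

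Power for arms a and b, when 83:83 gives 80%, is Φ(2.80 × √(4ab/166²) − 1.96). At 75:91 it is 79.6%. At 70:96, 4ab/166² = 0.975 and power is 79.0%. Overall imbalance therefore costs about 1 point or less.

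**Split within centres.** Assume c equal centres of m eyes, with m = 166/c rounded. For one centre, p = P(|2X − m| ≥ m/3) with X ~ Binomial(m, 0.5). For at least one centre, the chance is 1 − (1 − p)^c.

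| Centres | Eyes each | One given centre 2:1 or worse | At least one |
|---|---|---|---|
| 2 | 83 | 0.2% | 0.4% |
| 3 | 55 | 1.4% | 4% |
| 4 | 42 | 4.4% | 16% |
| 5 | 33 | 8.0% | 34% |
| 8 | 21 | 18.9% | 81% |
| 9 | 18 | 23.8% | 91% |
| 10 | 17 | 14.3% | 79% |

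The figures move with rounding because m is small: 4 centres of 41 give 11%.

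**Value of using centre.** Let ρ be the share of outcome variance between centres. The documents give no value, so 5% to 15% is assumed. With balanced centres and an adjusted analysis, the gain in effective eyes is 1/(1 − ρ) − 1:

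- ρ = 0.05: 5.3%
- ρ = 0.10: 11.1%
- ρ = 0.15: 17.6%

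Equivalently, power rises from 80% to Φ(2.80/√(1 − ρ) − 1.96), which is 82%, 84% and 86%.

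**Adjustment or stratification?** If centre is adjusted for but not stratified, the expected within-centre information falls from m/4 to (m − 1)/4 per centre. Variance rises by about 1/(m − 1): 1.2%, 3.1% and 6.3% for 2, 5 and 10 centres. The gain from adjustment alone is then 1/[(1 − ρ) × m/(m − 1)] − 1.

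- ρ = 0.15: 16%, 14% and 11% of the possible 17.6%.
- ρ = 0.05: 4%, 2% and about −1% of the possible 5.3%.

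Most of the gain comes from the analysis when centres are few or ρ is at the upper end. With many small centres and a small ρ, the blocks protect it. Stratified blocks followed by a plain t test would not collect it, because the test would still count centre differences as error.

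**The case against.** The strongest case is that nothing here is wrong. That stands. Three stronger readings are tempting, and the documents support none of them.

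- **A reader might infer that 7.5 contradicts itself**, because simple randomisation does not deliver a uniform distribution. The text is a translation, and *uniform* may mean only equal assignment probability. The sentence needs clarifying; it does not establish a false claim.
- **A reader might infer that the plan promises 83:83 and has a 6% chance of achieving it.** In 12.4, 83 is a sample-size target, and 7.2 fixes only the total. The power cost above shows how little rests on it.
- **A reader might infer bias or an inflated type I error.** Neither follows from simple randomisation or from ignoring centre after it.

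The size of the gain is also open to challenge. The between-centre share has no source in the documents. The formula is for a continuous outcome, while hyperemia is ordinal. Shared reference images limit grader differences. If change from baseline is analysed and the same grader scores each visit, stable differences partly cancel; 12.4 speaks of an increase, but section 14 does not define the comparison as a change and no section requires the same grader. These points reduce the gain without removing it. The observer argument applies to hyperemia and not in the same way to the other primary outcomes, which are a timed measure and a count of adverse events.

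**Conclusion.** The point holds as a cheap improvement to a valid design. Centre is recorded but used in neither 7.5 nor section 14, although a primary outcome is graded by eye at each centre.

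The cost is lost precision and possible chance imbalance within centres. The chance of at least one 2:1 split is under 1% with 2 centres and about 80-90% with 8 to 10. This assumes equal centres and independently allocated eyes. Unequal centres or bilateral subjects would change the figures.

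The precision at stake is about 5% to 18% of eyes. That rests on an assumed 5% to 15% between-centre share and a continuous-outcome approximation, and it is smaller if change from baseline is analysed.

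**What to change.** **In 7.5:** randomise subjects, not eyes, in permuted blocks of random size stratified by centre. The list should be prepared by the uninvolved individual who holds the codes under 7.3. With a block of 4, for example, arms differ by at most 2 subjects per centre. State whether both eyes of a bilateral subject receive the same allocation, and what *uniform distribution* means.

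**In section 14:** include centre in the primary hyperemia comparison, either as a factor in a model suited to the ordinal scale or through a centre-stratified test. Handle both eyes of a subject as one cluster. State how very small centres will be pooled.

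**Cost:** a new randomisation list, and a model or stratified test in place of the plain t or chi-squared test, which first requires the ordinal scale and the eye-or-subject unit to be settled. No extra patients are needed. Allocation becomes slightly more predictable, which random block sizes and masking limit. Stratification must be in place before enrolment; the analysis change can still be written in before unblinding.
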